9.4 Endpoint

In the present Clinical Investigation, the two variables chosen as *the primary and secondary endpoints* to measure the primary and secondary objectives of the Survey also coincide with the measures of response to treatment, in particular:

- Primary endpoint (security measure):

the safety of the *Chimaera* will be measured by the percentage of patients who within a 6-month observation period, due to serious adverse events related to *the Chimaera*, will have to undergo a second operation to continue with the treatment of the proximal femur fracture.

- Secondary endpoint (efficacy measure):

the effectiveness of the treatment carried out with *Chimaera* will be measured through the Bowers & Parker functional score for the evaluation of the patient's functional recovery.

Note:

Bowers & Parker's functional score⁷ It is a validated and unanimously recognized reliable score for the evaluation of patients treated following a hip fracture. This score assesses the patient's functional recovery (in terms of pain, walking ability and social independence) compared to the patient's condition before the fracture. The Bowers & Parker score also has predictive value for assessing the long-term mortality of the treated patient, and for planning short-term rehabilitation activities.

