9.5 Variables to measure

The primary endpoint (safety measure) of the present Clinical Investigation will be measured as follows:

- the correlation of the serious adverse event to the *Chimaera* will be freely assigned by the Investigator according to the following options: unrelated/potentially related/certainly related. Serious events potentially or certainly related to the *Chimaera* will be included in the calculation of the security measure.
- It is understood that, for serious events judged to be potentially or certainly related to the *Chimaera*, the Sponsor reserves the right to supplement the Investigator's assessment with an opinion from an independent orthopaedic physician and with a technical analysis of the implanted and removed device to proceed with the second intervention. Following these analyses, if the removed device complies with the design specifications, and if the independent orthopedist finds an operating technique error in the primary implant, in agreement with the Investigator, the event initially classified as potentially or certainly related to the *Chimaera* may be reclassified as unrelated and, therefore, will be excluded from the calculation of the safety measure. Similarly, serious adverse events due to use that does not comply with the manufacturer's instructions for use, otherwise referred to as *off label use*, will be excluded from the calculation of the safety measure.

The *secondary endpoint* (efficacy measure) of the present Clinical Investigation will be measured as follows:

- The Investigator will fill out a scale (Appendix 1) for each patient at each of the follow-up visits (1, 3, 6, and 12 months). If necessary, a translation of the scale into Italian is also provided to support comprehension.
- As suggested by the authors, the scale can be filled in by the Investigator on the basis of the answers provided by the patient, even by telephone. Given the type of patients that will be recruited, mostly non-self-sufficient elderly people who cannot always be moved easily, this procedure will not involve additional risks for the patient and should limit the number of patients that cannot be assessed due to lack of data on the secondary *endpoint*.

Data for the primary and secondary *endpoints* will be:

- reported in the patient's medical record and recorded in the electronic database provided free of charge by the Sponsor to each Investigator to collect the data of the Clinical Investigation;

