9.11 Medical-Surgical Procedures and Follow-up of the Clinical Investigation

After obtaining informed consent, the physician will include in the study those patients who, at the screening visit (Visit 0), meet all selection criteria. During the screening visit, the Investigator will also collect demographic data and the patient's medical history.

Enrolled patients, as would also occur if they chose not to participate in the present Investigation, will undergo the surgical procedure (Visit 1) required for the application of the investigational medical device (Chimaera), which marks the beginning of the treatment period.

Following the surgery, the patient will attend five subsequent visits. The first three visits after the surgical procedure are part of the treatment period and are:

- the visit performed at hospital discharge (Visit 2), which, unless complications occur, will take place within 10 days after the date of surgery. During this visit, the physician will perform routine assessments to confirm that the operation and postoperative course have proceeded appropriately;
- the following two visits (Visits 3 and 4), were conducted at 1 month and 3 months after the date of surgery, respectively. These visits conclude the treatment period which, in the absence of complications, is expected to be within 8–12 weeks from the date of surgery, with the consolidation of the treated proximal femoral fracture. Healing will be assessed by the Investigator through radiographic evaluation, performing a qualitative assessment of bone density at the fracture site and the alignment of the bone fragments. Starting from Visit 4 and at all subsequent visits, the Investigator will also complete the Bowers & Parker functional score (efficacy measure) to assess the patient's functional recovery.

For these patients, device removal is not planned unless required due to serious adverse events necessitating a second surgical procedure to complete the treatment of the fracture (safety measure). Once the treatment period is concluded, the follow-up period begins, during which two visits will be conducted (Visits 5 and 6), respectively at 6 months and 1 year after the date of surgery. During these visits, clinical data will be collected to monitor the progression of fracture consolidation, the patient's functional recovery, and the occurrence of any medium-term adverse events.

[figure not shown]

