9.12 Patient treatment schedule

9.13 Table of procedures applicable to each visit

PERIOD		ENROLMENT	TREATMENT				FOLLOW-UP	
VISIT	Number	Visit 0	Visit 1	Visit 2	Visit 3	Visit 4	Visit 5	Visit 6
	Type	Selection	Surgery	Discharge	1° Follow up	2° Follow up	3° Follow up	4° Follow up
	Window	Day 0 ± 1 week	Day 0	Day 5 ± 5 days	Month 1 ± 1 week	Month 3 ± 1 week	Month 6 ± 1 week	Month 12 ± 1 Month
Informed Consent		x						
Verification of Selection Criteria		x	x	x	x	x	x	x
Demographics		x						
Medical History		x						
Radiographic Examination		x	x			x		
Device Implantation			x					
Parker score						x	x	x
Safety Measures			x	x	x	x	x	x

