- copy of the approval of the Ethics Committee of reference;
- an original copy of the signed and approved economic agreement;
- list of participating centers;
- information regarding the medical device under observation (Instructions for use and surgical technique);
- certification relating to the CE marking of the device;
- patient information sheet and consent collection form;
- information letter for the attending physician;
- Adverse event reporting form;
- a copy of the data collection form;
- the eCRF access credentials and the platform user manuals.

Note:

The monitor will also deliver an electronic copy, non-modifiable, of all the study documentation for consultation and possible printing according to the needs of the Investigator.

As required by Good Clinical Practice guidelines:

- in order to prevent accidental or premature destruction of study documents, it will be the responsibility of the Investigator to keep the file in a secure environment with controlled access;
- for the entire duration of the clinical investigation, the study documentation must be updated and made available during the monitoring visits;
- the documentation relating to the study should be kept for the longest possible duration and, at least, for 7 years after the completion or conclusion of the Survey.

In the event that the Investigator relies on a third party for the preservation of the documents, he shall inform the Sponsor of the place of storage and the procedure for transferring the file.

12 Data management

No later than the study start visit, the Sponsor will provide an electronic data collection system (eCRF), called *Symphony*, free of charge, on which all data from this Clinical Investigation will be collected.

Symphony is an EDC (*Electronic Data Capture*) solution developed and validated by Arithmos Srl, which is an ISO 9001 and ISO 27001 certified company. *Symphony* therefore has an Information Security Management System in line with international regulatory standards and ensures compliance with regulations by monitoring and archiving the *audit history* directly on the platform.

For more details contact:

ARITHMOS Srl

[name]

[contact]

[contact]

[contact]

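### The efficacy score is presented as recovery relative to the pre-fracture condition, but the plan specifies no pre-fracture rating and no comparison with one

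*Combined protocol and SAP*

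**What the plan says.** Section 9.4 names the Bowers & Parker score as the secondary (efficacy) endpoint, a "functional score for the evaluation of the patient's functional recovery". The Note below it explains what the score is meant to show: "This score assesses the patient's functional recovery (in terms of pain, walking ability and social independence) compared to the patient's condition before the fracture".

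The places where a pre-fracture value would have to appear read as follows.

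- **Section 9.5** has the investigator complete the Appendix 1 scale at the 1, 3, 6 and 12 month visits.
- **Section 9.11** starts later: "Starting from Visit 4 and at all subsequent visits, the Investigator will also complete the Bowers & Parker functional score". Before surgery it provides only this: "During the screening visit, the Investigator will also collect demographic data and the patient's medical history".
- **The Section 9.13 table** marks the score at Visits 4, 5 and 6 only. Visit 0 has consent, selection criteria, demographics, medical history and radiograph.
- **Appendix 1** lists absolute levels for mobility (1 to 10), social dependence (1 to 8) and pain (0 to 8). It has no pre-fracture column and no instruction to rate earlier status by recall.
- **Section 18** plans the mean, standard deviation, median, minimum, maximum and 95% confidence interval of the score. It names no change from pre-fracture status and no proportion regaining it.

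In the pain domain of Appendix 1, 0 means that neither patient nor carer could answer, and 1 means no hip pain. Section 18 does not say how 0 is handled.

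**The concern.** The study has no control group (Section 9.2), so each patient's own earlier condition is the natural reference for recovery. Section 9.5 describes the expected patients as "mostly non-self-sufficient elderly people who cannot always be moved easily". If many of them already had limited function, a poor score at 3 or 12 months may reflect the fracture and its treatment, or may simply be where the patient started. A post-operative score alone cannot tell these apart.

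The protocol's own background uses the pre-fracture reference: Section 2 reports that 42% of survivors do not regain their earlier mobility. The data specified here could not be set beside that figure. Section 18 nevertheless intends the collected data to help confirm that the device is effective, so a reader may take a summary of status as a summary of recovery.

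**Working it through.** **What the plan's own figures cover.** No figure is stated for the secondary endpoint. Enrolment follows from the primary endpoint and the expected loss: 300 / (1 − 0.25) = 400, as stated. The Section 18 table reproduces with exact two-sided 95% limits; for example, 15 events in 250 give an upper limit of 9.703%. At 6% of 300 (18 events) the upper limit is 9.32%, below the 10% target. None of this depends on the score.

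**Count of ratings.** Pre-fracture ratings specified: 0. Post-operative ratings: 4 under Section 9.5 (months 1, 3, 6, 12) or 3 under Sections 9.11 and 9.13 (months 3, 6, 12).

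**What a follow-up score says about loss.** Mobility runs from 1 (best) to 10 (worst). Loss = follow-up score − pre-fracture score. If no patient ends better than before, each pre-fracture score lies between 1 and the follow-up score. With mean follow-up score M, the mean loss therefore lies between 0 and M − 1.

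| Mean follow-up mobility M | Possible mean loss |
|---|---|
| 4 | 0 to 3 |
| 6 | 0 to 5 |
| 8 | 0 to 7 |

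If improvement is allowed, the mean change lies between M − 10 and M − 1; for M = 6 that is −4 to +5. For a single patient, a score of 6 is full recovery if the earlier score was 6, and a 5-point loss if it was 1.

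**Proportion back to pre-fracture mobility.** A patient is back when the follow-up score is no worse than the pre-fracture score. The proportion is smallest when every pre-fracture score was 1; it then equals the share at level 1 at follow-up. The largest value is 100%. If 5%, 10% or 20% are at level 1 (assumed), the proportion lies between 5%, 10% or 20% and 100%.

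**Pain code 0 used as a number.** Let p be the share coded 0 and m the mean among those who answer. The reported mean is (1 − p) × m, a shift of −p × m. Both p and m are assumed, because the documents give neither.

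| p | m | Shift in mean |
|---|---|---|
| 10% | 2 | −0.10 × 2 = −0.2 |
| 20% | 3 | −0.20 × 3 = −0.6 |
| 30% | 4 | −0.30 × 4 = −1.2 |

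If p rises from 10% to 30% between visits while m stays at 3, the mean falls from 0.90 × 3 = 2.7 to 0.70 × 3 = 2.1. That is an apparent gain of 0.6 points with no change in pain.

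**The case against.** **The sentence describes the published instrument.** It stands in a Note. The endpoint definition and the objective in Section 9.3 promise only a functional score, not change from pre-fracture status. This is fair, and it makes a change of wording a legitimate remedy. But the definition itself speaks of recovery, and the Note tells the reader what recovery is measured against.

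**Repeated scores show a course.** Values from month 3 to month 12 can show post-operative improvement or decline. They still say nothing about the condition before the fracture, and Section 18 plans no within-patient change.

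**The consequences are limited.** The endpoint is secondary and descriptive, and Section 18 sets no hypothesis or threshold. The Section 9.5 phrase on dependency may describe patients during follow-up rather than before the fracture. Both points stand and limit the severity.

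**The bounds follow from the scale.** They would hold in any study without a baseline, and the lower bound on the proportion recovered needs every patient to have been at level 1. That is correct; the bounds show what the data cannot exclude, not what is likely.

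**Pain code 0 is a side issue.** Appendix 1 sets it apart from the rated levels, and Section 9.14 lets a companion answer, which should keep the share low. But Section 18 plans a mean and does not exclude the code.

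**Unseen material may fill the gap.** Medical history may include earlier mobility, and Section 11 lists "a copy of the data collection form" as a separate document that was not available. The synopsis and the Section 9.12 schedule were not visible either. The finding is therefore that the rating is not specified in the text at hand, not that it cannot be obtained.

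**Conclusion.** The concern holds. Following the plan as written does not give the comparison that Section 9.4 describes. The only efficacy endpoint would report functional status after surgery, compatible with anything from no loss to a mean loss of M − 1 mobility points when no patient improves on the earlier level.

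The conclusion rests on the visible protocol text. The numerical ranges are scale limits or illustrations with assumed shares and means. Handling of pain code 0 is a smaller, related gap. The matter should be fixed, but it affects only the interpretation of the secondary endpoint; the primary endpoint and the sample size stand.

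**What to change.** **Preferred change.** In Section 9.13, add the Appendix 1 scale at Visit 0, rated by recall for the time before the fracture and answered by the patient or a companion. It must not rate current status, since an inpatient could score 8 on social dependence simply for being in hospital. In Section 18, add:

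- within-patient change from pre-fracture status, by domain;
- the proportion back to the pre-fracture mobility and social-dependence levels at 3, 6 and 12 months, among survivors with both ratings;
- the numbers of deaths and of unrated survivors beside each summary.

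Flag proxy ratings and ratings recalled late. Consent may follow the emergency (Section 4.3), so the text should say how late a recalled rating is accepted and how patients already enrolled are handled.

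**Fallback.** Limit Section 9.4 to functional status at follow-up and make no claim of recovery relative to the pre-fracture condition. This needs wording only, but earlier disability stays mixed into the result.

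**In either case.** Add one sentence to Section 18 treating pain code 0 as missing in all summaries, with its count reported at each visit. Separately, reconcile the month 1 score in Section 9.5 with Sections 9.11 and 9.13.

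**Cost.** The preferred change needs one short three-domain form per patient, an eCRF page and new Section 18 text. Telephone answers (Section 9.5) and companion answers (Section 9.14) are already allowed. The drawbacks are recall and proxy error and a protocol amendment. If the amendment is classed as substantial, Section 15 suspends the investigation until new ethics opinions are issued.

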9.5 Variables to measure

The primary endpoint (safety measure) of the present Clinical Investigation will be measured as follows:

- the correlation of the serious adverse event to the *Chimaera* will be freely assigned by the Investigator according to the following options: unrelated/potentially related/certainly related. Serious events potentially or certainly related to the *Chimaera* will be included in the calculation of the security measure.
- It is understood that, for serious events judged to be potentially or certainly related to the *Chimaera*, the Sponsor reserves the right to supplement the Investigator's assessment with an opinion from an independent orthopaedic physician and with a technical analysis of the implanted and removed device to proceed with the second intervention. Following these analyses, if the removed device complies with the design specifications, and if the independent orthopedist finds an operating technique error in the primary implant, in agreement with the Investigator, the event initially classified as potentially or certainly related to the *Chimaera* may be reclassified as unrelated and, therefore, will be excluded from the calculation of the safety measure. Similarly, serious adverse events due to use that does not comply with the manufacturer's instructions for use, otherwise referred to as *off label use*, will be excluded from the calculation of the safety measure.

The *secondary endpoint* (efficacy measure) of the present Clinical Investigation will be measured as follows:

- The Investigator will fill out a scale (Appendix 1) for each patient at each of the follow-up visits (1, 3, 6, and 12 months). If necessary, a translation of the scale into Italian is also provided to support comprehension.
- As suggested by the authors, the scale can be filled in by the Investigator on the basis of the answers provided by the patient, even by telephone. Given the type of patients that will be recruited, mostly non-self-sufficient elderly people who cannot always be moved easily, this procedure will not involve additional risks for the patient and should limit the number of patients that cannot be assessed due to lack of data on the secondary *endpoint*.

Data for the primary and secondary *endpoints* will be:

- reported in the patient's medical record and recorded in the electronic database provided free of charge by the Sponsor to each Investigator to collect the data of the Clinical Investigation;
- they will be analyzed using descriptive and/or quantitative statistics and presented with their respective confidence intervals (more details in the Statistics section of this Protocol).

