9.6.1 Inclusion criteria

A patient will be considered eligible for participation if:

- directly or indirectly (through a legally acceptable representative), he/she has expressed the willingness to participate in the Investigation by signing and dating the informed consent form;
- he/she is at least 65 years of age at the time of signing the informed consent form;
- he/she has been diagnosed with a stable or unstable fracture in the pectrochanteric, intertrochanteric, or subtrochanteric region of the femur, not previously treated;
- in the opinion of the Investigator, he/she has a standard indication for surgical treatment with an intramedullary nail;
- the fracture will be treated with the short (length = 180 mm) Chimaera nail and one or two telescopic cephalic screws, in accordance with the manufacturer's instructions for use.

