9.15 Interruption and withdrawal of subjects from clinical investigation

A patient will be discontinued prematurely from the study if they do not complete the last protocol-scheduled follow-up visit due to any of the following causes:

- the patient withdraws consent to participate in the study;
- one of the inclusion criteria will be dropped or an exclusion criterion will occur;
- lack of response to treatment that generates an unacceptable risk for the patient and prevents the continuation of the treatment covered by this observational scientific research;
- onset of a serious adverse event that generates an unacceptable risk for the patient and prevents the continuation of treatment;
- the patient does not follow the procedures of the clinical protocol provided by his doctor;
- decision of the Investigator in the interest of the patient;
- patient no longer available (lost to follow-up);
- death of the patient during the study period.

Patients who are prematurely discontinued will be reported in the data collection form through the appropriate discontinuation visit. The Investigator will have the obligation to report to the Sponsor the patients who are prematurely discontinued and, if the patient is not assessable, or is discontinued before the end of the treatment period for supposed recovery scheduled for the control visit at the third month after the operation), may agree with the Sponsor on the replacement of the patient according to the following procedure.

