9.16 Patient replacement

Upon notification to the Sponsor, no later than the study recruitment period, non-evaluable patients, at the discretion of the Investigator, may be replaced with a patient who will be assigned a new and unique identification code.

Considering the high percentage of withdrawal usually found with this type of patient, this procedure has the sole purpose of increasing the probability of reaching the expected sample size in terms of evaluable patients. It is understood that the Sponsor will also collect, store and analyze data from prematurely discontinued and replaced patients.

10 Clinical investigation monitoring plan

In order to ensure the proper conduct of the study and the correct recording of study data, at least the following monitoring visits will be planned:

- study start visit;
- two monitoring visits during the active conduct phase of the study;
- Closing visit of the study.

It is understood that, if necessary, for example if numerous deviations from this Protocol occur on a Site,

the Sponsor reserves the right to carry out additional monitoring visits during the live phase of the study.

Prior to each visit, the monitor will contact the Investigator to check availability and schedule the date of the visit, after which they will send a written confirmation specifying the purpose of the visit and any documents to be made available.

On each visit, the monitor must:

- check the updating of the study documentation;
- verify that the Clinical Investigation is conducted and that the data are produced, recorded and communicated in accordance with this Protocol, the Code of Good Clinical Practice – GCP and the applicable legislation;
- verify the correctness of the data entered in the data collection form towards the source data;
- implement any corrective actions.

Note:

The Sponsor intends to monitor the totality of data reported in the informed consent forms, inclusion and exclusion criteria, variables related to study endpoints, and all information regarding serious or non-serious adverse events. If deemed appropriate and necessary, the other data from the study may also be monitored.

11 Clinical Investigation Documentation

During the study initiation visit, the monitor will provide the Investigator responsible for the clinical investigation with a file containing all the paper documentation necessary for the management of the study, namely:

- study protocol with related Synopsis and appendices;

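### Section 9.5 lets events graded as device-related leave the primary safety numerator but never enter it, and Section 18 commits to one rate only, so the plan does not commit to showing what the removals changed

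*Combined protocol and SAP*

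**What the plan says.** Section 9.4 defines the primary endpoint as the percentage of patients who, within 6 months and because of serious events related to the device, "will have to undergo a second operation to continue with the treatment of the proximal femur fracture". Section 9.5 has the Investigator grade each serious event as unrelated, potentially related or certainly related. The last two grades count.

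Section 9.5 then gives two ways for a counted event to leave the numerator.

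- **Technique error.** For events already graded related, "the Sponsor reserves the right to supplement the Investigator's assessment with an opinion from an independent orthopaedic physician" and with a technical analysis of the removed device. Reclassification applies "if the removed device complies with the design specifications", the independent orthopaedist finds an error of technique at the primary implant, and the Investigator agrees. The event then "may be reclassified as unrelated and, therefore, will be excluded from the calculation of the safety measure".
- **Off-label use.** Also excluded are "serious adverse events due to use that does not comply with the manufacturer's instructions for use". Nobody is named to make that attribution, and nothing is said about the denominator.

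Section 18 presents the primary endpoint as one percentage with a 95% confidence interval. It also says that no threshold for safety or effectiveness has been set, and that the data will serve to confirm that the device can be considered effective and safe.

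**The concern.** The review runs in one direction. Only events graded related can be re-examined; events graded unrelated have no matching review. Any mistaken removal can therefore only favour the device, and no opposite correction is available to offset it.

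With one committed figure, a reader of the results may be unable to tell a rate that was low on the Investigator's own grading from one that became low through removals. This matters because the figure is the primary endpoint, and because Section 18 sizes the study so that the figure can be set against literature rates of 3% to 10%. The plan does not say whether those rates excluded technique errors or off-label use, so neither version of the rate can be called the better match. That is a reason to show both.

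**Working it through.** **1. The plan's own figures.** The two-sided exact (Clopper-Pearson) 95% upper limit for x events in n patients is the 0.975 quantile of Beta(x+1, n−x). For the five rows of the Section 18 table:

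| x/n | Rate | Upper limit |
|---|---|---|
| 3/100 | 3% | 8.518% |
| 4/100 | 4% | 9.926% |
| 8/160 | 5% | 9.614% |
| 15/250 | 6% | 9.703% |
| 28/400 | 7% | 9.958% |

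All five match the plan. Enrolment also reproduces: 300/(1−0.25) = 400. The same interval is used below, with n = 300 (the evaluable target in Sections 9.7 and 9.14).

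**2. Effect of removals in one data set.** The documents give no number of removals, so the counts are assumed, with one event per patient. Start from 18 graded events, since 0.06 × 300 = 18.

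| Removed | Left | Rate | 95% CI |
|---|---|---|---|
| 0 | 18/300 | 6.0% | 3.6 to 9.3% |
| 1 | 17/300 | 5.7% | 3.3 to 8.9% |
| 2 | 16/300 | 5.3% | 3.1 to 8.5% |
| 4 | 14/300 | 4.7% | 2.6 to 7.7% |

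Around the planning target of an upper limit below 10%, 20 events give 10.11% and 19 give 9.71%. One removal can move the limit across it.

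**3. Effect on the chance of meeting the planning target.** With n = 300 the target is met when the count is 19 or fewer. If each graded event is removed independently with probability q, the reported count is Binomial(300, p(1−q)), where p is the graded rate. Section 18 expects no more than 6% for the primary endpoint and does not say whether that is before or after removals. Both readings are shown.

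| q (assumed) | If 6% is the graded rate: reported rate | Chance that reported limit < 10% | If 6% is the post-removal rate: graded rate 6%/(1−q) | Chance that graded limit < 10% |
|---|---|---|---|---|
| 0 | 6.0% | 65% | 6.0% | 65% |
| 0.05 | 5.7% | 73% | 6.3% | 57% |
| 0.10 | 5.4% | 80% | 6.7% | 47% |
| 0.20 | 4.8% | 91% | 7.5% | 26% |

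On the second reading, the reported rate itself keeps a 65% chance throughout. At a graded rate of 5%, the reported chances are 88%, 92%, 95% and 98%. At 4% they run from 98.1% to 99.8%, which is a negligible difference.

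**4. Off-label denominator.** Section 9.6.1 makes use "in accordance with the manufacturer's instructions for use" an inclusion criterion. Section 9.15 discontinues a patient if "one of the inclusion criteria will be dropped or an exclusion criterion will occur". Section 9.16 says that "the Sponsor will also collect, store and analyze data from prematurely discontinued and replaced patients". Read together, these do not say whether off-label patients stay in the primary denominator. Assume that 15 of 300 patients are off-label and hold 3 of the 18 events. Removing events only gives 15/300 = 5.0%; removing the patients as well gives 15/285 = 5.3%. With 5 off-label patients holding 1 event, the figures are 17/300 = 5.7% and 17/295 = 5.8%.

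**5. Why both rates need one denominator.** Suppose the graded rate used 400 implanted patients and the primary rate used 300 evaluable patients. Then 18/400 = 4.5% before removals would stand beside 15/300 = 5.0% after them, and the removals would appear to raise the rate.

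**The case against.** The strongest reply is that the technique-error route is pre-specified and well guarded. It needs a conforming removed device, an independent orthopaedist's finding and the Investigator's agreement. A reader might infer that the sponsor can delete events alone, but on this route it cannot. On a plain reading, a second operation that leaves the device in place does not qualify at all. This stands, but it bears on whether removals are right, not on whether they are visible, and the off-label route states no such conditions.

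A reader might also infer that the reported rate will be biased. The documents do not support that. The endpoint is device-related by definition, potentially related is a broad grade, and removals may be correct.

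Nor is off-label use unchecked. The Section 9.13 table verifies selection criteria at every visit, Section 10 plans full monitoring of those criteria, and Section 14 has deviations classified and their effect on interpretation reviewed at study end. The gap is narrower: nobody is named to attribute an event to off-label use.

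Finally, nothing bars the sponsor from listing removed events in the final clinical report. That is true, and for that reason the point is that the plan makes no commitment, not that the information will be hidden. A choice made once results are known is weaker than a commitment made now.

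**Conclusion.** The point holds as a reporting gap in the primary endpoint. On a common denominator, the planned rate can only equal or fall below the Investigator-graded rate, and the plan does not commit to showing by how much. With 300 patients and 18 graded events, removing 1 to 4 lowers the rate by 0.3 to 1.3 percentage points. These counts are assumed, because the documents give none.

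Two stronger readings should be avoided. One is that removals could turn a failed study into a successful one: there is no hypothesis test and no threshold, and 10% is only a sizing target. The other is that the plan's expected 6% gains from 65% to as much as 91% through removals. That follows only if 6% is a pre-removal rate, which the documents do not say. The off-label denominator is a minor part, about 0.1 to 0.3 points in the examples above. Overall this is a cheap improvement, not a fatal flaw.

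**What to change.** Keep the Section 9.5 rate as the primary result. In Sections 9.5 and 18:

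- Commit to reporting beside it the rate on the Investigator's original grading (potentially or certainly related), on the same stated denominator and with an exact 95% confidence interval.
- Commit to a list of every reclassified or excluded event, with the route and the reason.
- Name who attributes an event to off-label use, drawing on the selection-criteria checks, monitoring and deviation list already planned in Sections 9.13, 10 and 14.
- Add a supplementary on-label rate that takes off-label patients out of both numerator and denominator, using a list fixed without regard to outcome. Label it as a different estimand, because Section 9.5 removes only events due to off-label use.

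The cost is protocol wording, one table and a short listing. Section 9.5 already has endpoint data entered in the database, and Section 10 plans monitoring of all adverse event information, so no extra patients or visits are needed. If the planned checks do not settle off-label status for every patient, the on-label rate will need some further assessment. The downside is that a possibly less favourable rate stands beside the headline, with a sentence to explain that it includes technique-related and off-label events.
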